## **INTRODUCTION:**

750,000 Canadians have dementia from Alzheimer Disease or other causes, this number will double within the next generation, and no new therapies have emerged in the past 20 years. However, a new promising therapy is transcranial direct current stimulation (tDCS), a near painless treatment where mild electrical current is applied through the scalp to the brain. This has been found to improve symptoms in people with dementia. Unfortunately, some studies have also reported that tDCS failed to improve symptoms in their participants, so it's important to understand why tDCS seems to work in some cases, but fails to produce an improvement in other cases. One possible reason is the intensity level of tDCS, which is normally 2 mA in studies. Some researchers believe a higher intensity level, 4 mA, would produce a bigger improvement.

## **LITERATURE REVIEW:**

Symptomatic therapy in neurodegenerative diseases (NDD) is very limited. Since introduction of the cholinesterase inhibitors in 1995 and Memantine in 2002, there have been no new available pharmaceutical therapies. As a result, researchers are looking beyond chemicals for a means to ameliorate cognitive impairment. Neuromodulation, particularly tDCS has garnered increasing attention as a potential ancillary symptomatic brain therapy for neurological and psychiatric conditions, reaching the level of being made clinically available for pain and depression [1, 2].

In tDCS, two electrodes (anode and cathode) are secured to the scalp and continuous current flows through the brain from anode to cathode, which modulates corresponding neural activity. It has been theorized that if these neuronal pathways are activated to a certain level, a long-lasting change will occur in the network which allows information to be more easily retrieved or remembered. Consistent with this hypothesis, recent studies at a few centers have shown clinically meaningful improvement in individuals with neurodegenerative diseases treated with transcranial direct current stimulation (tDCS). For instance, we have previously shown a robust effect of improved picture naming [3-4] in individuals with Primary Progressive Aphasia (PPA) and people living with dementia who also suffered from anomia [5]. We have also published case reports where tDCS improved the quality of life in an individual with advanced dementia [6] and walking speed in a person with Progressive Supranuclear Palsy [7]. Others have found similar results [8-10]. We have shown that anomia (picture naming deficits) is improved with seven to ten daily half-hour sessions of tDCS along with language training, for both AD and FTD [3-7, 28, 32-34], with effects lasting several weeks.

Despite these encouraging results, studies examining tDCS for people with dementia have produced variable results. For example, Khedr et al. [11] reported positive tDCS effects, whereas Cottelli et al.[12] and Suemoto et al.[13] reported no improvement or equivalence to a placebo condition. Neuromodulation, however, is both diverse and relatively recent, with differences between approaches, techniques, and electrode montages across studies, making it difficult to compare results. As reported by Prehn and Flöel [14] in their review of tDCS for people with dementia: “The most effective stimulation parameters for enhancing cognitive function in older subjects and patients with AD and MCI are still unclear.”

Our research has increasingly focused on identifying the parameters that increase efficacy. For example, in our previous study [5], we found a montage focused on the parietal lobe was superior to one focused on the dorsolateral prefrontal cortex (DLPFC) for improving naming ability. Finding such parameter optimizations is critical for advancing tDCS as a therapy for people with dementia as we learn to tailor its administration. In the current project, our central goal is to examine a critical additional stimulation parameter: intensity.

**RATIONALE:**

tDCS studies typically report significant group effects despite the variability demonstrated among participants, with some showing clear, meaningful improvement, while others only show statistical improvement or none at all. These variable results may be related to the conventional stimulation intensity level of 2mA. Recent evidence suggests an electric field of at least one v/m is needed to affect local networks in the brain [15] reliably. However, tDCS at 2mA produces an electric field around only 0.6 v/m because a large amount of shunting (a dilution of the incoming current) occurs as the current travels from the electrode on the scalp, through the skin, skull, and cerebral spinal fluid (CSF), before reaching the brain. The most direct way to increase the electric field produced in the brain is to increase the intensity delivered. Current tDCS machines can have an intensity level of 4mA, resulting in more substantial electric fields than one v/m. We predict that if we were to administer tDCS at 4.0 mA, a more significant number of participants would show a meaningful response, and those who improve at 2mA may improve even more from 4.0mA due to having a larger electric field produced.

We aim to test this hypothesis in people with Alzheimer's Disease because they have unique attributes that may impact tDCS differently from other populations. More specifically, the amount

of shunting is predicted to be larger due to increasing CSF from brain atrophy [16]. Thus, 2mA may be too weak to be very effective in some people with Alzheimer's Disease due to the higher level of shunting. More significant improvements would be observed from a higher intensity level that can better interact with the remaining cortex. Alzheimer's Disease is also predominately female, and past studies have suggested men and women respond differently to tDCS [17-24]. For example, women have smaller skulls than men in general, which are predicted to receive more of the incoming stimulation. Finally, as Alzheimer's Disease is progressive, the degree of impairment may be relevant [25]. We will check if individuals who are more impaired benefit more when the stimulation intensity is set higher. The level of impairment will be measured in two ways: (1) the baseline score on a naming task (baseline severity); and (2) scores collected from cognitive testing (cognitive severity).

### **Purpose of the Research**

tDCS has the potential to emerge an effective ancillary symptomatic therapy for Alzheimer's Disease. However, the optimal tDCS parameters are unknown, improvement varies from person to person, and we cannot presently predict who will most benefit from tDCS. The proposed project aims to fill this knowledge gap by investigating how different variables impact the effectiveness of tDCS. In this manner, the proposed project will provide a significant step forward towards finding the optimal participants for treatment as well as the optimal tDCS delivery method for people with AD. This work, using a proven naming task, is an essential step towards future random clinical trials investigating tDCS as therapy for people with AD.

## **Hypotheses Addressed**

The degree of improvement observed in people with Alzheimer's disease will be significantly greater when training is carried out at higher stimulation intensity (4mA vs. 2mA, SHAM).

There will be significantly more significant improvement observed when:

[figure not shown]
1. Individuals have more atrophy (decreased brain volume, higher CSF volume).
2. Individuals have a higher degree of impairment
3. The participant is female (possibly due to skull differences).

## **PRELIMINARY STUDIES**

The proposed study models after our original three-round study [5] where three different tDCS montages were compared for improving naming ability. We recently completed another three-round study [28] where a mixed group of people with dementia (AD and FTD) concluded three consecutive rounds of executive function training with either: 4mA tDCS targeted towards the left dorsolateral prefrontal cortex (DLPFC), 2mA tDCS via two anode electrodes to the left and right DLPC respectively, or SHAM stimulation, which is the accepted placebo condition in tDCS studies. In SHAM stimulation, tDCS is only briefly active at the beginning and end of the session, which mimics the real-life sensation of tDCS as feelings are felt mainly only at the beginning and end of the session when the current is ramping up or down. We measured how much participants improved on an N-Back task, defined as having faster response times. For evaluation, participants completed two versions of this N-Back task: one practiced during the tDCS sessions, and another never practiced and was only given during evaluations. For trained items, results were similar regardless of stimulation condition, but for untrained items, the largest improvement was found for 4mA tDCS (see Figure 1 below). 4 mA tDCS was also well tolerated with no adverse effects among the 24 individuals who participated. Building on this work, we now propose to carry out a training

paradigm to compare 4 mA, 2 mA, or SHAM, but using picture naming, a domain we have already shown to improve with tDCS in our previous studies [4-6], with tDCS again targeting the Inferior Parietal Lobe (IPL).

Figure 1:

## METHODS:

### Sample

Based on the previous study where tDCS was used for language training [6], we expect a partial eta square around 0.20. For 80% power to detect a difference across the three levels of intensity, while also accounting for the sex of a participant, a repeated-measures ANOVA test at an alpha level of 5% will require 54 participants with AD (27 men and 27 women). To compensate for anticipated attrition over the study, we will recruit a sample of 30 men and 30 women, 60 total.

These participants would have received the diagnosis of probable AD from Baycrest's Memory Clinic expert staff [29, 30] according to standard clinical criteria. Only patients with no family history of epilepsy and who can give consent will be tested. We will seek people with mild to

moderate AD (Reisberg stages 3, 4, or 5, [34]) who score between 18 and 25 on the MoCA [26]. Participants must show no history of stroke or traumatic brain injury, nor shunts or metal in the head that could interfere with the delivery of tDCS. Finally, people will have no evidence of significant heart disease, alcoholism, drug use. All enrolled participants will be expected to complete an MRI; however, if they are unable to complete an MRI due to the presence of an exclusion criterion, they will still be allowed to complete all subsequent stages of the study. Participants will be evaluated and trained using different naming lists each round. We have developed equivalent versions of these naming lists in our lab, which allows us to use a different trained and untrained list each round.

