### **Planned Analyses**

The primary outcome measure will be improvement on the naming lists administered, both a trained version and an untrained version. Improvement will be measured in terms of the number

of images correctly named post-training compared to baseline. A repeated-measures ANOVA will be run to compare the three stimulation conditions (SHAM, 2mA, 4mA) with sex (male, female) as a between-subject variable. This analysis will be conducted separately for the trained and untrained items. We expect to find the greatest improvement in the 4mA condition.

Next, we will calculate how much a participant improved in each condition by taking the naming score obtained at baseline for a naming list and subtracting it from the naming score obtained in the final stimulation session (e.g., 32 (final) – 20 (baseline) = an improvement score of 12). These scores are then used to produce tDCS effectiveness scores: the improvement score in the 4mA condition minus the improvement score in the SHAM condition; and the improvement score in the 2mA condition minus the improvement score in the SHAM condition. These tDCS effectiveness scores will then be the dependent variables in a multivariate logistic regression; once for trained items, one for untrained items. The predictors will be the CSF level of a participant, grey matter volumes and skull thickness around the IPL, impairment scores (baseline and cognitive severity), and interactive terms representing the sex of the participant. In this manner, we can examine what individual differences predict the tDCS response in people with AD, and if these predictors are the same for 2mA and 4mA tDCS, while checking for sex differences. We expect more significant levels of CSF, less IPL grey matter, thicker skulls, and greater impairment levels will be predictive of more substantial improvement in the 4mA condition because this stimulation intensity is needed to compensate for higher levels of shunting and severity. CSF and grey matter values may be less predictive for how well women respond to tDCS as their relatively smaller heads could compensate for increased shunting levels.

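### The required sample size of 54 does not follow from the inputs stated for it, and its effect size is credited to a report on one person

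*Protocol*

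**What the plan says.** The Sample section names its source, "Based on the previous study where tDCS was used for language training [6"], and its effect size: "we expect a partial eta square around 0.20". The aim is given as "For 80% power to detect a difference across the three levels of intensity", "while also accounting for the sex of a participant", and the conclusion is that "a repeated-measures ANOVA test at an alpha level of 5% will require 54 participants with AD (27 men and 27 women"). Recruitment is raised to 60 for attrition.

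Planned Analyses describes the matching test: "A repeated-measures ANOVA will be run to compare the three stimulation conditions (SHAM, 2mA, 4mA) with sex (male, female) as a between-subject variable". It is run separately for trained and untrained items. Neither section gives a correlation between conditions, a sphericity correction, an effect-size convention, or how sex enters the power calculation.

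On reference 6, the Literature Review says: "We have also published case reports where tDCS improved the quality of life in an individual with advanced dementia [6"]. The title of entry 6 in the reference list likewise concerns a single person.

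**The concern.** A sample-size sentence that gives effect size, power, alpha and test, and then says what N these require, should be reproducible from those inputs, at least to within the usual conventions. This one is not. A reader cannot tell whether 54 comes from a sound calculation with an unreported setting or from a wrongly entered effect size.

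The source adds to the doubt. A partial eta squared for a group comparison needs a group, and the reference cited has one participant. The required N depends strongly on this input. On the usual reading it is 96 for a partial eta squared of 0.05, 48 for 0.10, 32 for 0.15 and 24 for 0.20.

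**Working it through.** **Inputs.** From the Sample section: partial eta squared 0.20, power 80%, alpha 5%, 27 men and 27 women. From Planned Analyses: three within-subject conditions, and sex as a between-subject factor with two levels.

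**Effect size.** f² = 0.20 / (1 − 0.20) = 0.25, so f = 0.50.

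**Attempt to reproduce 54, usual reading.** Partial eta squared is taken as the ANOVA reports it. For intensity, and equally for sex by intensity, df1 = 2ε, df2 = 2(N − 2)ε and λ = f² × 2(N − 2)ε. Power is the upper tail of the noncentral F beyond its 5% critical value. N is the smallest even number that reaches 80%.

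| ε | Minimum N | Power there | Power at N = 54 | Partial eta squared detectable with 80% power at N = 54 |
|---|---|---|---|---|
| 1 | 24 | 82.6% (N = 22: 78.4%) | 99.7% | 0.087 |
| 0.75 | 28 | 81.3% | 98.6% | 0.105 |
| 0.5 (floor for three levels) | 36 | 80.8% | 94.3% | 0.135 |

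At N = 54 and ε = 1, λ = 0.25 × 2 × 52 = 26. The stated 54 is not reproduced at any ε.

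**Other conventions using only the stated inputs.** With λ = f² × N and sphericity, the need is 42. A multivariate test gives 42 to 46. Powering each sex alone under sphericity gives 22 per sex, 44 in total. None of these gives 54.

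**Routes that do give 54, each with an unstated choice.**

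- f² = 0.25 entered as f = 0.25, with zero correlation: λ = 0.0625 × 3 × N. N = 54 gives 80.9% and N = 52 gives 79.2%. At 54, λ = 10.125. Setting this equal to f² × 104 gives f² = 0.0974, a partial eta squared of 0.0974 / 1.0974 = 0.089. This route powers for 0.089, not 0.20.
- Each sex powered alone with ε = 0.75: λ = 0.25 × 2(n − 1) × 0.75. n = 27 per sex gives 81.3% and n = 26 gives 79.6%. The minimum is 27 only for ε between about 0.72 and 0.76.
- λ = f² × N × ε with ε = 0.65: N = 54 gives 80.0%. Under this convention the need is 50 at ε = 0.75 and 66 at ε = 0.5.

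**Attrition.** 54 / (1 − 0.10) = 60, so the step to 60 is consistent with an implied 10% loss.

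**The source of 0.20.** The Literature Review and the reference list both make reference 6 a single-person report. tDCS Parameters and Training Sessions attach the naming training to reference 5, so a citation slip is plausible. Preliminary Studies, however, says that reference 5 compared three montages. An effect size from it would describe a montage contrast, not an intensity contrast.

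**What the omnibus power implies for 4 mA versus 2 mA.** The documents give no pattern of means, so the pattern must be assumed. At N = 54, with omnibus 0.20 and sphericity, the contrast has df 1 and 52, and its λ is a share of 26:

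| Assumed pattern | Share of λ | Power |
|---|---|---|
| 4 mA equals 2 mA | 0 | 5% |
| Means equally spaced | 1/4 (6.5) | 71% |
| SHAM equals 2 mA | 3/4 (19.5) | 99% |

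**The case against.** The strongest reply is that the stated inputs do not fix a single N. Correlation, sphericity, noncentrality convention and the role of sex are all open, and a separate SAP may supply them. One legitimate route also fits the wording: the answer is given per sex, and powering each sex with a modest nonsphericity allowance gives 27. This stands in part. The figure of 24 belongs to one convention, though the usual one, and silence on such settings would not by itself be a fault. But the protocol states a definite result from definite inputs. No convention that uses those inputs alone reaches it, and the per-sex route needs ε in a narrow window that is nowhere stated.

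Three stronger readings are tempting and not supported. First, a reader might infer a specific input error, such as f² entered as f. It gives 54, but so do other routes, and the document does not choose between them. Second, a reader might infer that the trial is oversized. That would take 0.20 as established, and its cited source cannot establish it. Third, a reader might infer that the contrast in Hypotheses Addressed, "significantly greater when training is carried out at higher stimulation intensity (4mA vs. 2mA, SHAM"), is underpowered. The Sample section claims power only for a difference across the three levels, and the contrast's power runs from 5% to 99% with the assumed means.

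The citation may well be a one-digit slip. It still needs correcting, because the present source cannot have produced the number.

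**Conclusion.** The point holds in two parts. First, 54 is not the N that partial eta squared 0.20, 80% power and alpha 5% require for the ANOVA described. The need is 24 on the usual reading (28 at ε = 0.75, 36 at ε = 0.5) and 42 with λ = f² × N under sphericity. On the usual reading 54 gives 99.7% power (94% at ε = 0.5), so the discrepancy is conservative for the omnibus test. This rests on complete data, equal numbers of each sex and the noncentral F approximation. Second, the effect size is credited to a one-person report, which cannot supply it; this part does not depend on any power convention. What is shown is a figure that cannot be traced and an effect size without a valid source. A shortage of power is not shown.

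**What to change.** Rerun the calculation and restate the sentence so that effect size, power and N agree. Name the test powered (pooled omnibus or each sex alone), how sex enters, the effect-size convention, and the correlation or epsilon actually used. An epsilon should not be chosen after the fact to recover 54.

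If the pooled omnibus test was meant, say that 54 completers give 80% power for a partial eta squared of about 0.087 (0.105 at epsilon 0.75, 0.135 at epsilon 0.5). If f = 0.25 was entered, give that as the effect size powered, in place of partial eta squared 0.20.

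Replace reference 6 with the group study that gave 0.20, and say which contrast that value describes; if it is reference 5, say that the contrast was between montages. For a pooled calculation, state that the power figure applies to the omnibus test of intensity only. If a figure for 4 mA versus 2 mA is wanted, give a range over stated patterns of means, not one number.

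The cost is a text change. Recruitment of 60, the design and the analysis stay as they are.

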### **Recruitment and Pre-Assessment**

All participants are recruited following the same enrollment protocol: Initial contact, screening, and pre-assessment. For *the initial contact*, the research coordinator will receive names of potential participants from the Clinical Trials Unit at Baycrest. The files of these individuals will be acquired from Sam & Ida Ross's Memory Clinic. Their contact information and diagnosis will be noted. They will then be contacted using a prepared telephone script. Those individuals who show interest in the study will then be scheduled a screening with [name] [name].

This *screening* can be done in person at Baycrest, or virtually over Zoom, and the participants can choose a particular modality if they have a preference. During the screening, [name] will go over the consent form with the participant, including the mechanics, history, and side-effects of tDCS, and the planned study design (i.e., what participation would entail schedule-wise). The screening also allows [name] to evaluate subjectively if the person may be too impaired for the study (for example, if they are unable to communicate or answer questions during the screening). If this scenario were to arise, [name] would explain to the participant, and

presumed caregiver, that the person is too impaired for the study. The screening is also an opportunity for the potential participant to ask any questions they might have. Assuming the participant is agreeable to participating in the study, a pre-assessment will be scheduled.

[figure not shown]
In this *pre-assessment*, the participant will be asked to complete versions of the tasks that will be administered during the study. In this manner, we can further verify that the potential participant is a good candidate for completing the study. Assuming they are able to successfully complete the tasks during the pre-assessment, and continued to be interested in participation, he or she would then be formally enrolled and scheduled into the study. Otherwise, the participant would be explained that they are unable to be enrolled into the study because they are unable to successfully complete the tasks planned. Because tDCS is an interactive therapy (a targeted behaviour must occur while the stimulation is administered), it is crucial that participants be able to complete the planned tasks, and simply receiving tDCS passively (i.e., while doing nothing) would be largely, if not completely, ineffective.

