### **Structural MRI Protocol**

Participants will undergo a Structural MRI at Baycrest. The protocol has been informed to the MR Technicians (please see attached documents). The Project Coordinator will book the MR suite using the Baycrest MR Web Scheduler with a 72 hour notice at the least.

Participants will be asked to arrive 15 minutes before their scheduled scan to review and fill the consent and MR screening forms. The participant will then be escorted to the Interview room to be interviewed by a Level 11 MR Personnel with respect to their MR screening form and medical history prior to changing for the MR exam. After changing, the MR technologist will escort the research participant into the magnet room and the accompanying researcher (Assistant, Coordinator or PI) to the control area. Post scanning, the lab member accompanying the research participant will monitor the change process, and other processes outlined in the "MR Research Suite Process Baycrest – RRI."

To be able to successfully perform the MRI, lab members will undergo the Virtual MR Safety Training & Orientation session and will also receive an in person suite tour.

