### **Risks**

The tDCS protocol for this experiment was determined according to the best practices observed in previous research using tDCS stimulation [45]. Furthermore, tDCS is safe, has virtually no side effects, is technically easy to carry out, and is not uncomfortable to undergo [46,47]. Multiple studies have also reported that the administration of 4 ma tDCS has no more adverse effects than 2 ma tDCS [48]. No incidence of seizure has been recorded, although side effects could include headache, drowsiness, itching sensation, nausea, and, in rare cases, disorientation. In our experiences, the only observed and reported side-effect has been temporary redness post-stimulation where the sponge was placed, as well as the occasionally reported headache.

If the event were to result in lasting pain and hospitalization, then it would be reported as a 'Serious Adverse Event' and full details would be noted to the research ethics board as well as Health Canada. These events would be recorded on the worksheets being used to collect the rest of the data. We must stress, however, that after administering 4 mA tDCS to around 60 participants, for hundreds of tDCS sessions, we have never encountered any such event. Although we have safety protocols in place for any encountered adverse or severe adverse events, we believe such events will fail to occur in the present study.

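### The only epilepsy criterion concerns relatives; no shown eligibility text covers a participant's own epilepsy, although every participant is scheduled for a 4mA round

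*Protocol*

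**What the plan says.** The eligibility rules stand in the protocol under Methods, Sample. The epilepsy rule is one sentence: "Only patients with no family history of epilepsy and who can give consent will be tested". The remaining medical exclusions follow in the same section: "Participants must show no history of stroke or traumatic brain injury, nor shunts or metal in the head", and "Finally, people will have no evidence of significant heart disease, alcoholism, drug use".

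Recruitment and Pre-Assessment describes the route to enrolment. From the clinic files, "Their contact information and diagnosis will be noted". Candidates are then telephoned with a prepared script, screened in person or by video, and given a pre-assessment. Enrolment follows on this condition: "Assuming they are able to successfully complete the tasks during the pre-assessment, and continued to be interested in participation".

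Under Study Design, each participant completes three rounds, one each at SHAM, 2mA and 4mA.

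The Risks section is the only place that mentions seizure: "No incidence of seizure has been recorded, although side effects could include headache, drowsiness, itching sensation, nausea".

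**The concern.** An epilepsy criterion in a brain-stimulation study has an obvious purpose: to limit seizure risk during stimulation. A criterion that looks only at relatives does this indirectly and leaves the direct case unaddressed. If a relative's epilepsy is reason enough to exclude a candidate, silence about the candidate's own epilepsy is hard to reconcile with that reason.

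Participant safety is at stake. Because the design is within-subject, the gap is not confined to a third of the sample. Anyone admitted through it is scheduled for both active intensities, including the higher one. Eligibility is fixed in the protocol, so this is not a matter that a statistical analysis plan would settle.

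**Working it through.** No arithmetic applies. The check is whether any shown text would exclude a person who has epilepsy and no affected relative.

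**Step 1: the criteria themselves (Sample).**

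| Listed criterion | Excludes a person with their own epilepsy and no affected relative? |
|---|---|
| Family history of epilepsy | No; it concerns relatives |
| Capacity to consent | No |
| Disease stage and MoCA range | No |
| Stroke or traumatic brain injury | No, unless one of these is also present |
| Shunts or metal in the head | No, unless also present |
| Significant heart disease, alcoholism, drug use | No, unless also present |

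For stroke and brain injury, the same section refers directly to the participant's own history. For epilepsy it does not.

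**Step 2: two candidates, alike on every other criterion.**

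- Candidate A has a sibling with epilepsy and does not have epilepsy. A fails the epilepsy criterion and is excluded.
- Candidate B has epilepsy and no affected relative. B passes the epilepsy criterion and every other listed one, and is eligible.

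**Step 3: later steps that might stop candidate B.**

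- *Initial contact.* The information said to be noted from the clinic file is contact details and diagnosis. The telephone script is mentioned but not reproduced.
- *Screening.* As described, it covers the consent form, side effects, the schedule, and a subjective view of whether the person is too impaired.
- *Pre-assessment.* It turns on whether the person can do the study tasks and remains interested.
- *Initial Assessment.* It lists demographic items, MoCA, MMSE, the naming task and the MRI. No medical-history item is listed.
- *Structural MRI Protocol.* This is the only medical-history interview described: the participant is "interviewed by a Level 11 MR Personnel with respect to their MR screening form and medical history". It serves the scan. For people who cannot have the MRI because of an exclusion criterion, the Sample section says "they will still be allowed to complete all subsequent stages of the study". Failing MRI screening therefore does not keep anyone from stimulation.
- *Risks.* Seizure appears in a safety statement, not as a condition of entry.

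**Step 4: exposure.** Under Study Design, each participant is scheduled for one round at each intensity, so candidate B would be scheduled for 2mA and 4mA as well as SHAM.

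**Result.** No shown text excludes candidate B, while candidate A is excluded by name.

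**The case against.** The best reply is that this is a drafting slip. The authors may have meant personal and family history, and clinic staff may turn away people with epilepsy in practice. That is plausible, but the protocol does not say so, and the written criterion governs who is eligible. If it is a slip, correcting it is all the easier.

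The second reply is that the telephone script may already ask about seizures. This stands in part. The script is not shown, and the recruitment section lists none of its questions, including any on stroke or metal in the head. A reader might infer that screening asks nothing about seizures. The documents do not support that; they show only that the protocol describes no such question. Even if the question is asked, the criterion as worded gives no ground for excluding someone on the answer.

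Four other stronger readings are also tempting and should not be drawn:

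- *That the protocol admits the people at highest risk and removes those at lower risk.* The documents give no seizure risk by personal or family history. The inconsistency follows from the evident purpose of the criterion and needs no risk ranking.
- *That the safety case rests on no seizure having occurred.* In Risks, seizure takes up half a sentence. The reassurance rests mainly on previous research, on cited reports comparing 4mA with 2mA, and on the team's own experience with around 60 participants at 4mA.
- *That a seizure would end that person's data.* No withdrawal rule after a seizure is stated, and Confidentiality says that data from people who withdraw are kept unless they withdraw consent for its use. At most, later rounds might be missing.
- *That a count of affected participants can be given.* Multiplying the planned 60 by an assumed prevalence has no anchor in the documents. It would also ignore the other exclusions that some of these people would meet.

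**Conclusion.** The point holds as a gap in a stated safety criterion. Family history of epilepsy is an exclusion, the participant's own epilepsy is not, and nothing else shown closes the gap. Followed literally, the rule does not serve its evident purpose.

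The size cannot be stated as a number, because the documents do not say how common epilepsy is among the clinic's patients. What can be said is that the consequence for anyone admitted this way is scheduled exposure to both active intensities.

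The conclusion rests on two assumptions. The first is that the criterion is meant to limit seizure risk; the protocol does not state this, but no other purpose is apparent. The second is that the unseen material (the telephone script, the consent pages and the missing figures) does not add an eligibility rule that the Sample section omits. The point does not claim that harm is likely or that the omission was deliberate.

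**What to change.** Correct the epilepsy criterion under Sample so that it expressly addresses the participant's own history of epilepsy as well as family history. What counts as a relevant history is a clinical decision for the sponsor, and no scope is proposed here. In particular, nothing in this point calls for widening the family-history rule beyond epilepsy.

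Then reconcile three sections: Sample (the criterion), Recruitment and Pre-Assessment (where and how it is checked before enrolment) and Risks (how seizure is described). Since MRI screening does not decide who receives stimulation, the check should not rest on the MRI interview.

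The cost is one phrase in the protocol, one screening check if the script does not already contain it, and possibly a few candidates lost to recruitment. The design and the planned analyses do not change.
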